10.5.2 Follow-up of Adverse Events

All AEs considered to be related to study treatment will be followed until resolution or stabilization.

10.6 Collection and Reporting of Serious Adverse Events

10.6.1 Initial Serious Adverse Event Reports

All SAEs that occur from the time of informed consent up to and including 60 days after the last dose of study treatment must be reported by the Investigator to the Sponsor or Sponsor's designated representative immediately, and in no circumstances later than 24 hours after gaining awareness of the event by submission of a SAE Notification Form. Investigators must report to the Sponsor or the Sponsor's designated representative any SAE, whether or not considered drug related, including those listed in the protocol or Investigator's Brochure. The initial report must contain at a minimum a subject identifier code, an event term, and an assessment of causality. The SAE Notification Form should be faxed or e-mailed to:

[REDACTED]
[REDACTED]
[REDACTED]
[REDACTED]

If the Investigator is unable to complete and send the SAE Notification Form within the timeframe required, the SAE must be reported via phone call to the Medical Monitor (see contact sheet in the study reference binder) and [REDACTED].

An Investigator may be requested by the Sponsor or the Sponsor's designated representative to obtain specific follow-up information in an expedited fashion. This information may be more detailed than that captured on the Adverse Event eCRF. In general, this will include a description of the SAE in sufficient detail to allow for a complete medical assessment of the case and independent determination of possible causality. Information on other possible causes of the event, such as concomitant medications and illnesses must be provided. In the case of a subject

death, a summary of available autopsy findings must be submitted as soon as possible to the Sponsor or the Sponsor's designated representative.

10.6.2 Follow-up of Serious Adverse Events

All SAEs should be followed up until resolution or stabilization. The timelines and procedure for follow-up reports are the same as those for the initial report.

New information regarding an SAE that becomes available after the submission of the initial SAE Notification Form must be reported by the Investigator to the Sponsor or the Sponsor's designated representative by completion of a SAE Follow-up Report Form or through other written documentation (e.g., laboratory tests, discharge summary, postmortem results). Follow-up reports and/or written documentation must be provided to the Sponsor or the Sponsor's designated representative immediately, and no later than 24 hours after the Investigator's receipt of the information.

10.7 Post-Trial Adverse Events

Any AE that occurs outside of the protocol-specified observation or after the end of the trial but is considered to be caused by the study treatment must be reported to the Sponsor or the Sponsor's designated representative.

10.8 Pregnancy Reporting and Follow-up

Pregnancy in a female clinical trial subject is not an SAE per se. Complications of such pregnancies, for example, spontaneous abortion, may qualify as an SAE and should be reported as an SAE even if they occur after the SAE reporting period has ended.

The Investigator must notify the Sponsor via telephone or e-mail immediately, and no later than 24 hours after awareness of a pregnancy in a study subject and must complete the Pregnancy Notification Form and submit it to the Sponsor within 2 working days of being notified. The subject will not receive any further doses of their assigned study treatment and will be permanently discontinued from study treatment. The pregnancy must be followed to determine outcome, including spontaneous or voluntary termination, details of birth, and the presence or absence of any birth defects, congenital abnormalities, or maternal and/or newborn complications. This follow-up should occur even if the intended duration of safety follow-up for the trial has ended. Information regarding the course of the pregnancy, including perinatal and postnatal offspring outcome up to 8 weeks of age should be reported as follow-up information on the Pregnancy Notification Form.

Male study subjects will be instructed to notify the Investigator if a female partner becomes pregnant during the study. The Investigator must notify the Sponsor immediately and no later than 24 hours via telephone or e-mail and must complete the Pregnancy Notification Form and submit it to the Sponsor within 2 working days of being notified. The Investigator should obtain informed consent from the subject's partner allowing the Investigator to obtain information regarding the pregnancy and its outcome. If the subject's partner provides informed consent, the Investigator should follow the pregnancy until outcome as described above for female study subjects and report the follow-up information on the Pregnancy Notification Form.

10.9 Study Termination

The Sponsor may suspend enrollment or terminate the study at any time for safety concerns or other reasons.

10.10 End of Study Definition

The end of the study is defined as the timepoint when all study subjects meet at least one of the following criteria:

1. Confirmed progression in the randomized period for subjects randomized to cobomarsen
2. Confirmed progression in the randomized period for subjects randomized to vorinostat who choose not to participate in the crossover period
3. Confirmed progression in the crossover period
4. Full withdrawal of consent or lost to follow-up
5. Death
6. Duration on the study (from randomization) of at least 3 years.

or, the study is terminated early by the Sponsor.

10.11 Emergency Sponsor Contact

In a medical emergency (i.e., an event that requires immediate attention regarding operation of the clinical study and/or the use of investigational drug), study site staff will apply appropriate medical intervention according to current standards of care, and contact the Medical Monitor (see contact sheet in the study reference binder) or the designated Sponsor representative, as indicated in [Section 1](#) of this protocol.

11 TRIAL-SPECIFIC COMMITTEES

11.1 Data Monitoring Committee

The Data Monitoring Committee (DMC) will be responsible for reviewing safety data at regular intervals as well as to perform the interim analysis. A separate DMC Charter will be established that outlines DMC membership, precisely what data will be reviewed, along with the timing and frequency of the reviews. DMC recommendations will be provided to the Sponsor in compliance with the DMC Charter.

11.2 Steering Committee

The study Steering Committee (SC) will be appointed by the Sponsor prior to the initiation of the study. The SC will include principal investigators from the study and Sponsor representatives. The SC will be involved in the oversight of the study and will ensure transparent management of the study according to the protocol through recommending modifications as circumstances require. Details on the role of the SC and working procedures will be defined in the SC Charter.

12 STATISTICAL CONSIDERATIONS

12.1 Statistical and Analytical Plans

Final statistical analysis will be completed after the last subject completes or discontinues the study and the study database has been cleaned, verified, and locked. Based on timing of the primary and secondary endpoints, additional interim database locks may occur, before the final database lock.

A statistical analysis plan (SAP) will be completed prior to the database lock. This document will provide a technical and detailed description of the data analysis methods and procedures.

The results of the final analysis will be presented in the clinical study report. Any deviations from planned statistical analyses will be presented in the clinical study report.

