 - More than 3 short courses (≤ 7 days) of prednisone equivalent > 10 mg per day within 8 weeks prior to Screening; however, a stable regimen of systemic prednisone equivalent to ≤ 10 mg per day (or steroid equivalent) is permitted;
 - Any CTCL systemic therapy after completion of the randomization period and prior to Day 1 for the crossover period.

6. Positive test for blood (including trace) on urinalysis considered by the investigator to be consistent with undiagnosed clinically significant renal pathology requiring further investigation.
7. An active or uncontrolled infection defined as subjects who require systemic antibacterial, antiviral, or antifungal therapy within the last 7 days prior to Screening.
8. Clinically significant anemia (hemoglobin < 8 g/dL), neutropenia (absolute neutrophil count [ANC] < 1000/mm³) or thrombocytopenia (platelets < 50,000/mm³) at Screening.
9. Presence on ECG of QT interval corrected for heart rate using Fridericia's formula (QTcF) > 450 msec for males or > 470 msec for females or > 480 msec for subjects with bundle branch block, based on a mean of the triplicate ECG measurements collected at Screening.
10. Unwillingness to comply with study procedures, including follow-up, as specified by this protocol, or inability to communicate or cooperate fully with the Investigator.
11. Lactating or pregnant.
12. Major surgery within 4 weeks of the first dose of study treatment.
13. Unable to understand the purpose and risks of the study and to provide a signed and dated informed consent form (ICF) and authorization to use protected health information (in accordance with national and local subject privacy regulations).
14. Clinically significant abnormalities in medical history, physical examination, or laboratory values that, in the opinion of the Investigator, would make the subject unsuitable for inclusion in the crossover period.
15. History of intolerance, or adverse or allergic reactions to oligonucleotide products and/or phosphate buffer solutions.

Statistical Methods:

Details of statistical testing and data summaries will be described in the Statistical Analysis Plan, which will be finalized prior to database lock.

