The analysis of the primary efficacy endpoint is the proportion of subjects in the randomized period achieving an ORR4 in skin by mSWAT assessments. The statistical test for the primary efficacy endpoint will be one-sided and will be split between the interim and final analysis and conducted using a total 0.025 significance level. Additional details of the primary efficacy endpoint in addition to the secondary efficacy endpoints will be detailed in the statistical analysis plan.

	
Safety analyses will include AEs, concomitant medications, laboratory data, physical examination, and ECG data.
 
The following analysis populations will be defined:
 
Intent to Treat Analysis Set (ITT)
 
The ITT will include all randomized subjects who received at least one dose of study treatment (cobomarsen or vorinostat) and had at least one post-baseline assessment.
 
Safety Set
 
The Safety set will include all randomized subjects who received at least one dose of study treatment (cobomarsen or vorinostat).
 
Per Protocol Set (PPS)
 
The PPS will consist of all subjects randomized to the study, who received study treatment, and completed assessments necessary for the evaluation of the primary endpoint with no major protocol deviations that would affect endpoint analysis.
 
Pharmacokinetic Analysis Set (PKAS)
 
The PKAS will consist of subjects randomized to cobomarsen who received at least one dose of cobomarsen and had at least one post baseline PK sample taken and analyzed.

Sample Size Justification:
	
Total enrollment of approximately 126 subjects randomized 1:1 provides greater than 80% power to detect a 25% difference (35% vs 10%) in the primary outcome, ORR₄, between the investigational product and active comparator groups.

Planned Interim Analysis:
	
An interim analysis will be performed after approximately 40 subjects are followed for a minimum of approximately 6 months.

Trial-specific Committees:
	
Data Monitoring Committee
 
The Data Monitoring Committee (DMC) will be responsible for reviewing safety data at regular intervals as well as to perform the interim analysis for futility. A separate DMC Charter will be established that outlines DMC membership, precisely what data will be reviewed, along with the timing and frequency of the reviews. DMC recommendation will be provided to the Sponsor in compliance with the DMC Charter.

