4 STUDY DESIGN

This is a Phase 2, randomized, open-label, parallel-group, active comparator, multi-center study to assess the efficacy and safety of cobomarsen compared to vorinostat in subjects with MF (Figure 1). The randomization will be stratified based on subjects with at least one skin tumor at Screening vs. no skin tumors at Screening. Subjects will also be stratified based on prognostic factors (age at diagnosis > 60 years and lactate dehydrogenase [LDH] level > the upper limit of normal [ULN] at diagnosis) (Scarlsbrick et al., 2015). Subjects will be stratified based on having 0-1 vs 2 of these prognostic factors.

[figure not shown]
This study will have 2 periods, a randomized period and a crossover period. Subjects who are on the vorinostat arm in the randomized period and have confirmed skin disease progression may elect to participate in the crossover period of the study.

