12.3 Analysis Datasets

Assignment of subjects to analysis sets will be done prior to database lock. The following analysis sets will be defined: the Intent to Treat analysis set (ITT), the Safety set, the Per Protocol Set (PPS), and the PK Analysis Set (PKAS).

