12.4.7 Planned Interim Analyses

An interim analysis will be performed after approximately 40 subjects are followed for a minimum of approximately 6 months to allow assessment for a 4-month duration of response (ORR4) from the date of initial objective response. A decision to stop the study at interim analysis for superiority will be considered if the one-sided test statistic p-value is < 0.01 (Pocock, et al. 1977). The number of skin ORR4 events required to demonstrate superiority at the interim analysis are shown in [Table 6](#).

Table 6: ORR4 Events Required to Demonstrate Superiority in Skin Objective Response for Interim Analysis ($p < 0.01$)

Vorinostat (N = 18)	Cobomarsen (N = 18)
0/18	6/18
1/18	8/18
2/18	10/18
3/18	11/18
4/18	12/18
5/18	13/18
6/18	14/18
7/18	15/18
8/18	16/18
9/18	17/18
10/18	18/18
11/18	18/18
12/18	18/18

Enrollment will be halted if data from this study or other cobomarsen studies conclusively demonstrate that cobomarsen does not have significant activity in MF.

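### The SAP is due only before an unspecified database lock, so analysis details the protocol leaves open or contradictory could be settled after the interim ORR4 comparison

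*Combined protocol and SAP*

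**What the plan says.** **SAP deadline.** Section 12.1 states: "A statistical analysis plan (SAP) will be completed prior to the database lock". The synopsis (Statistical Methods) agrees: "Details of statistical testing and data summaries will be described in the Statistical Analysis Plan, which will be finalized prior to database lock". Section 12.1 also says that "additional interim database locks may occur, before the final database lock", but not which of these locks governs the SAP.

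**What is left to the SAP.** The synopsis adds: "Additional details of the primary efficacy endpoint in addition to the secondary efficacy endpoints will be detailed in the statistical analysis plan".

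**The interim look.** Section 4 describes the trial: "This is a Phase 2, randomized, open-label, parallel-group, active comparator, multi-center study". Section 12.4.7 states: "An interim analysis will be performed after approximately 40 subjects are followed for a minimum of approximately 6 months". It continues: "A decision to stop the study at interim analysis for superiority will be considered if the one-sided test statistic p-value is < 0.01". Table 6 gives the responder counts needed at 18 per arm. Section 11.1 assigns the interim analysis to the DMC under a separate charter.

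**What the protocol already fixes.** Section 12.4.3 defines ORR4 and Appendix F gives the skin response criteria. Section 12.2 names a CMH test using the randomization strata. Sections 12.4.7 and 12.5.1 give 0.01 at the interim, 0.015 at the end and 0.025 in total, all one-sided.

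**The concern.** A deadline of database lock protects an analysis when nobody sees comparative results until then. Here a comparative efficacy result is produced when about a third of the sample (40/126 = 32%) has been followed, and enrollment is paused for it. Nothing in the documents requires the SAP to exist at that moment.

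This would matter little if the protocol settled every choice. It does not: on five points that affect who counts as a responder, who is in the denominator, or which p-value meets which threshold, it is silent or gives two answers. If those answers are chosen once the interim result is known, the stated error rates no longer describe the procedure actually used. Section 12.1 promises to report deviations from planned analyses, but a choice first made in a late SAP would be the plan and would not be listed as a deviation.

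**Working it through.** **Step 1. Reproduce the plan's power figure.** Inputs from section 12.5.1: 63 per group, 35% v 10%, one-sided 0.015, pooled Z with continuity correction. The mean rate is 0.225.
- Null SE = √(2 × 0.225 × 0.775 / 63) = 0.0744.
- Alternative SE = √(0.35 × 0.65/63 + 0.10 × 0.90/63) = 0.0710.
- Power = Φ[(0.25 − 1/63 − 2.170 × 0.0744) / 0.0710] = Φ(1.02) = 84.7%.

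This agrees with the stated figure of more than 80%. SAP timing does not affect it.

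**Step 2. Set the open items side by side.**

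| Item | One place | Another place |
|---|---|---|
| Interim test | 12.2: stratified CMH | 12.4.7 names no test; Table 6 follows Fisher (step 3) |
| Final threshold | 12.2: 0.025 | 12.5.1: 0.015 |
| Population | 12.5.1: all randomized | 12.3.1: dosed, with a post-baseline assessment |
| Missing ORR4 | 12.4.1: no imputation unless stated | No rule for a subject whose response cannot be assessed |
| Confirmation | 7.5.1.2: a visit within 28 days (± 3) | 12.4.3: no less than 28 days (± 3) later |

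**Step 3. Interim test.** I found the smallest winning cobomarsen count at 18 per arm and one-sided p < 0.01, for 0 to 12 vorinostat responders. One-sided Fisher reproduces 12 of the 13 rows of Table 6. The exception is 10/18, where 17/18 already gives p = 0.0089 but the table asks for 18/18. A CMH-type test needs only 5, 7, 9, 10 and 11 responders against 0 to 4; Table 6 asks for 6, 8, 10, 11 and 12. The CMH-type test is unstratified because the documents give no stratum sizes.

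For 1/18 v 7/18:
- Fisher: p = [C(18,7) × 18 + C(18,8)] / C(36,8) = (572,832 + 43,758) / 30,260,340 = 0.0204.
- CMH-type: pooled rate 8/36; SE = √(2 × 0.2222 × 0.7778 / 18) = 0.1386; z = (6/18 / 0.1386) × √(35/36) = 2.37; p = 0.0089.

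The same data miss the boundary by one test and cross it by the other. Under Fisher, 1/18 v 8/18 is needed (p = 0.0089).

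**Step 4. Final threshold.** Treat the interim and final statistics as bivariate normal with correlation √(40/126) = 0.563. Overall alpha = 0.01 + final alpha − P(both cross).
- Final 0.015: 0.01 + 0.015 − 0.0021 = 0.0229.
- Final 0.025: 0.01 + 0.025 − 0.0029 = 0.0321.

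With 36 subjects at the interim instead of 40, the values are 0.0231 and 0.0323.

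**Step 5. What a late choice could do (illustration only).** Assume the more favorable of two final analyses is chosen, each at 0.015, with test statistics correlated between 0.80 and 0.98. Overall one-sided alpha then runs from 0.031 down to 0.026. The correlation is an assumption; the documents give nothing from which to estimate it.

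**The case against.** The strongest reply is that the protocol is itself the pre-specification. ORR4, the response criteria, stratified CMH, the strata, the alpha split and the Table 6 counts are all written down, and section 13.4 allows protocol changes only by approved amendment. That stands: it confines the point to the five items in step 2. It does not close them, because a SAP that picks one of two protocol statements needs no amendment.

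Table 6 can also be read as a fixed interim rule, and its mismatch with CMH would need reconciling whenever the SAP were signed. That is fair. Likewise, the 0.025 in section 12.2 may be meant as the total level, as in the synopsis. But section 12.2 uses 0.025 as the criterion for significance and for stepping down to PFS, without mentioning the 0.015.

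The lock in question might be an interim one, which would narrow the gap. The text neither says so nor rules it out.

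A reader might infer four stronger things that the documents do not support:
- *The whole primary analysis could be written after the look.* It could not, for the reasons above.
- *Arm-level results are visible throughout because treatment is open-label.* Open-label means that individual assignments are known. It does not show that ORR4 is tabulated by arm for those writing the SAP. The DMC charter may restrict access but is not among the documents, and they state no firewall, so sponsor access cannot be asserted either way.
- *The choice of interim test shows lost error control, since at 35% v 10% the chance of crossing is 19.9% by Fisher and 30.8% by the CMH-type test.* Those are probabilities under the alternative. Under equal rates of 10% to 35%, false crossing at 18 per arm is about 0.001 to 0.005 for Fisher and 0.005 to 0.011 for the CMH-type test, so either test alone stays at or close to 0.01.
- *Undefined crossover outcomes affect the primary result.* They are separate secondary endpoints (section 3.2.2), and section 12.4.3 confines the primary analysis to the randomized period.

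**Conclusion.** The point holds as a gap in timing. Under sections 12.1 and the synopsis, a SAP signed after the interim ORR4 comparison would comply with the plan, and five items that bear on the decision are not settled elsewhere. The clearest error-rate exposure is the final threshold: overall one-sided alpha of about 0.023 if 0.015 governs, and about 0.032, above the 0.025 claimed, if 0.025 is applied at the end. The interim test can reverse a decision on identical data (0.020 v 0.009 at 1/18 v 7/18), but neither test used alone inflates the interim error much.

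The population, missing-data and confirmation items cannot be sized, because the documents give no expected rate of undosed, unassessed or unconfirmed subjects. The alpha figures rest on a normal approximation and an information fraction of 40/126. The CMH-type figures ignore stratification. Sample size and power do not change, and nothing here suggests that choices would be made in bad faith. The change should be made because the exposure is avoidable at almost no cost.

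**What to change.** Amend section 12.1 and the synopsis to require that the SAP, or an interim SAP, be signed and dated before the interim data cut and before any efficacy summary by arm is produced. It should cover ORR4 derivation, missing ORR4 data, analysis sets, and the tests and thresholds for the interim and final analyses. Later changes should be dated and listed as post-interim in the clinical study report.

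In the same amendment, reconcile:
- section 12.2 with 12.5.1 on the final threshold;
- section 12.2 with 12.4.7 and Table 6 on the interim test, including the 10/18 row;
- section 12.3.1 with 12.5.1 on the population;
- section 7.5.1.2 with 12.4.3 on confirmation timing.

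State in section 12.4.1 or 12.4.3 how a subject with missing ORR4 data is counted.

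The cost is earlier SAP sign-off. No subjects, visits or data are added, and the planned enrollment pause at about 40 subjects gives a natural checkpoint.
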